4.2.2 Rationale for Dose Selection/Regimen/Modification

The selection of doses and regimens to be administered in this study is based on safety and pharmacodynamic measures obtained in P001 and P002 in healthy subjects and P003 in subjects with T2DM and obese healthy subjects and known characteristics of GLP-1 agonists. The two doses of MK-8521 studied (180 μg and 300 μg) will offer better understanding of any potential dose response relationship with regards to safety (increase in HR and GI intolerance) and efficacy (glucose reduction and weight loss) endpoints.

In P003, administration of 300 μ g MK-8521 resulted in an exposure of 66.5 nMhr in subjects with T2DM. Treatment of subjects with T2DM with 300 μ g/ day MK-8521 was associated with a placebo-adjusted mean increases in HR TWA_{0-24hr} of ~ 8.3 bpm and a liraglutide 1.8 mg-adjusted mean increase in HR TWA_{0-24hr} of ~2.46 bpm. GI AEs occurred in 15/18 (83.3%) subjects with T2DM exposed to MK-8521 in Part 2 of P003 and were generally mild. No clear relation between dose and GI AEs was identified and no discontinuations from study medication due to GI AEs occurred with MK-8521. Glucose lowering was similar between 300 μ g MK-8521 and 1.8 mg liraglutide. The LS mean change in 24hr WMG with 300 μ g MK-8521 was -53.4 mg/dL vs. -59.7 mg/dL with liraglutide, and the change in FPG was -52 mg/dl for both liraglutide 1.8 mg and MK-8521 300 μ g. In P003, doses equal to or higher than 120 μ g MK-8521 and 1.2 mg liraglutide were associated with near maximal glycemic effects.

The rationale for having a higher dose and lower dose arms is primarily to study the dose-response of safety and efficacy parameters of different doses of MK-8521. The lower dose arm of 180 μg is expected to provide sufficient enhancement of glucose-dependent insulin secretion to achieve notable changes in A1C. Based on modelling and data obtained in prior studies, this dose should be well tolerated and associated with a placebo-adjusted mean increases in HR TWA_{0-24hr} of \sim 7 bpm that is expected to be similar to the change in HR with liraglutide 1.8 mg. Gastrointestinal intolerance (presenting as nausea, vomiting etc.) can occur with GLP-1 agonist therapy and may be partially mitigated by dose titration [13]. In keeping with this notion, a dose escalation/titration regimen will be implemented in the current trial.

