4.2.3 Rationale for Endpoints

4.2.3.1 Efficacy Endpoints

Efficacy endpoints will be assessed after 12 weeks of daily dosing and will include change in glycemic parameters and change in body weight.

Glycemic efficacy endpoints will include the changes from baseline in A1C and FPG at Week 12. A1C reflects average glucose concentrations over the past 3-4 months and, therefore, provides a useful index of the glycemic control of treatment with MK-8521 over that time period. It is a standard efficacy endpoint used to assess the glycemic efficacy of AHAs. A1C is a key glycemic parameter which correlates with reduction of risk of diabetic microvascular complications. The measurement of FPG will provide in sight into the effects of treatment with MK-8521 on this endpoint and characterize the earlier time course of glucose control in this trial.

Body weight reduction is an anticipated outcome of co-activation of GLP-1R and GCGR. Body weight loss may also drive A1C reduction at a modeled rate of 0.1% reduction in A1C for every 1 kg reduction in body weight. While the trajectory of reduction in A1C achieved with GLP-1R activation (as observed with liraglutide) reaches near maximal efficacy at 12 weeks, further potential weight loss past 12 weeks with MK-8521 may lead to further reduction in A1C. Data regarding body weight loss collected throughout the 12 week treatment period will be used to model further weight loss and subsequent A1C reduction up to 24 weeks.

Other efficacy endpoints that will be assessed include changes from baseline at Week 12 in fasting plasma lipid profile (including LDL-cholesterol, HDL-cholesterol and triglycerides), and blood pressure. These are clinically meaningful metabolic endpoints that may change

Protocol/Amendment No.: 004-02

with body weight loss. Moreover, glucagon receptor activation has previously been implicated in several studies as causing a reduction in LDL-cholesterol.

Efficacy endpoints obtained from both MK-8521 arms will be interpreted vs. placebo and vs. results collected in the liraglutide-treated arm.

There exist limitations of the comparisons to liraglutide, as liraglutide will be dispensed as an open label medication and MK-8521 as blinded. Data may be confounded by subjective assessments, compliance, or other affects based upon subject and investigator knowledge of the assigned therapy in the liraglutide arm. To mitigate these effects, previously published liraglutide data will be taken into account.

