7.1.2 Clinical Procedures/Assessments

7.1.2.1 Vital Signs (Sitting Blood Pressure and Heart Rate)

Vital sign measurements include a triplicate measurement of sitting blood pressure and heart rate. Blood pressure and heart rate will be measured using an automated, oscillometric blood pressure measuring device at all visits as noted in the Trial Flow Chart - Section 6.0. Site personnel should use the same blood pressure measuring device throughout the study for each subject.

The following method should be used to record sitting blood pressure and heart rate for subjects in triplicate:

- Subjects will refrain from ingesting caffeine for at least 10 hours preceding the measurements.
- Subjects should be seated in a chair with their back supported, feet flat on the floor and arm bared (free of restrictions such as rolled up sleeves) and supported at heart level
- The appropriate cuff size must be used to ensure accurate measurement. Each subject's cuff size should be noted in his/her source file to assure the same cuff size is used throughout the trial.
- Measurements should be taken on the same arm at each visit (preferably the non-dominant arm).
- Measurements should begin after at least 5 minutes of rest.
- The three measurements of both the blood pressure and heart rate must be taken approximately 2 minutes apart.
 - Note: Measurements will be collected until the 3 consecutive systolic BP readings do not differ by more than 5 mm Hg of each other and the 3 consecutive diastolic BP readings do not differ by more than 5 mm Hg of each other with the last triplicate set recorded in the eCRFs.
 - The mean (average) of the last triplicate set of BP readings (at Visit 1 and if necessary, at Visit 3) will be used to determine eligibility.

Protocol/Amendment No.: 004-02

 Assessment of heart rate can be manual (rather than using an automated device); however, when done manually, heart rate must be measured in the brachial/radial artery for at least 30 seconds.

- Note: Measurements will be collected until the 3 consecutive heart rate readings do not differ by more than 5 bpm of each other with the last triplicate set recorded in the eCRFs.
- The mean (average) of the last triplicate set of heart rate readings will be used to determine eligibility (Visit 1, Visit 2, and Visit 3), baseline HR (Visit 3), and discontinuation criteria (all post-randomization visits).

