8.2.3.2 Safety Endpoints

Safety and tolerability will be assessed by a clinical review of all relevant adverse experiences and monitoring variables related to blood chemistry, hematology, vital signs, and ECG.

Tier 1 safety endpoints are adverse events of symptomatic hypoglycemia (see Table 13).

Tier 2 safety endpoints include changes from baseline in HR at different time points.

Adverse events (overall summary, specific AEs, and AEs by system organ class) and PDLCs in laboratory and vital signs parameters (including proportion of subjects with HR>100 bpm or HR increase > 30 bpm) will be classified as belonging to "Tier 2" or "Tier 3", based on the number of events observed.

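### Section 7.1.2.1 requires device-measured heart rate but also allows unrestricted, unrecorded manual counts, so HR change can mix methods and MK-8521 versus liraglutide is open to observer bias of unknown size

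*Combined protocol and SAP*

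**What the plan says.** Section 7.1.2.1 opens with a general rule: "Blood pressure and heart rate will be measured using an automated, oscillometric blood pressure measuring device at all visits". It then adds "Site personnel should use the same blood pressure measuring device throughout the study for each subject", and fixes cuff size and arm for each subject. Further down the same procedure list comes the alternative: "Assessment of heart rate can be manual (rather than using an automated device", on condition that "heart rate must be measured in the brachial/radial artery for at least 30 seconds". No visit, reason, site or arm is named as a limit. Nothing ties a subject to one HR method, and the section does not ask for the method to be captured; only the last triplicate set goes to the eCRF.

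The mean of that set determines eligibility, "baseline HR (Visit 3), and discontinuation criteria (all post-randomization visits". On the analysis side, Section 8.2.3.2 states that "Tier 2 safety endpoints include changes from baseline in HR at different time points", and Section 8.2.5.2 compares each MK-8521 dose with placebo and with liraglutide, giving 95% confidence intervals for Tier 2 endpoints. HR change is also among the interim safety endpoints (Sections 2.1 and 8.2.9.2).

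Section 5.2.3 makes liraglutide open-label to sponsor, investigator and subject. Section 4.2.1 names HR among the reasons for including that arm.

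**The concern.** The consistency rules cover the blood pressure device, the cuff and the arm, but not the way HR is obtained. A subject may have a device value at the Visit 3 baseline and a finger count at Week 12, or the reverse, and the Section 7.1.2.1 data would not show it.

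A manual count also turns an instrument reading into one that depends on an observer. In the MK-8521 and placebo arms that observer is blinded. In the liraglutide arm the observer may know both the treatment and that HR is a class effect of interest, and the documents provide no blinded vital-signs assessor. When discussing the liraglutide comparison in Section 4.2.3.1 (an efficacy section), the protocol itself warns: "Data may be confounded by subjective assessments, compliance, or other affects based upon subject and investigator knowledge of the assigned therapy". For HR this exposure is largely avoidable, since the device is already required at each of these visits.

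At stake is the interpretation of HR change for MK-8521 against liraglutide, a safety comparison the trial was partly set up to inform. The A1C, weight and FPG analyses are not affected.

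**Working it through.** The plan gives no SD, precision or power for HR, so there is no stated figure to reproduce. The check sets the text side by side and then gauges scale.

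**1. What the wording permits (Section 7.1.2.1)**

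| Item | Fixed per subject? |
|---|---|
| Blood pressure device | Yes |
| Cuff size | Yes |
| Arm | Yes |
| HR method (device or manual) | No |
| HR method recorded | Not requested |

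**2. Which errors survive into the comparison**

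- A method offset that is constant within a subject cancels in change from baseline.
- If subjects switch method at the same rate in every arm, the offset cancels in the mean difference between arms but adds variance. Suppose baseline is always by device, follow-up is manual with probability p, and the offset is d. The added variance is p(1 − p)d². With p = 0.5 and an assumed d = 2 bpm, this is 0.25 × 4 = 1 bpm², an SD of 1 bpm. Without an SD for HR change, the loss of precision cannot be stated.
- An observer effect that comes from knowing the treatment does not cancel. Visit 3 HR is exclusion criterion 42 (Section 5.1.3), so it must be read before randomization, when nobody knows the arm. Such an effect could enter only the post-baseline readings, and only in the liraglutide arm.

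**3. Scale of a manual count**

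- Resolution at the 30-second minimum: 60/30 = 2 bpm per beat. A longer count is finer.
- Random rounding, assuming uniform error: 2/√12 = 0.58 bpm per reading, and 0.58/√3 = 0.33 bpm for a mean of three. This is small, so granularity alone is not the problem.

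**4. Illustrative size of a systematic shift**

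If a fraction f of follow-up readings in one arm is manual with mean shift b, and the other arm has no such shift, the bias in the difference is f × b. Both f and b are assumptions. The reference is the liraglutide "1.8 mg-adjusted mean increase in HR" of about 2.46 bpm from P003 (Section 4.2.2).

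| b (bpm) | f | Bias (bpm) | Share of 2.46 |
|---|---|---|---|
| 1 | 0.25 | 0.25 | 10% |
| 1 | 1.0 | 1.0 | 41% |
| 2 | 0.5 | 1.0 | 41% |
| 2 | 1.0 | 2.0 | 81% |

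The 2.46 bpm is a 24-hour time-weighted average, whereas the trial endpoint is sitting clinic HR, so these shares show order of magnitude only. Section 4.2.2 also gives placebo-adjusted increases of about 8.3 bpm (300 µg, observed) and 7 bpm (180 µg, expected). Against those, 2 bpm would be 2/8.3 = 24% and 2/7 = 29%, but the placebo comparison is blinded and this mechanism does not reach it.

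**The case against.** The strongest reply is that the bullet is an ordinary permitted alternative with its own conditions (artery and minimum duration), and that nothing shows manual counts will be common or that subjects will switch. That is correct. The absence of a limit on visit or reason is read from silence, and the point concerns what the text leaves open.

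Existing safeguards also count:

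- Section 5.9 calls for an ECG when an HR discontinuation criterion is suspected, so a pulse count alone should not settle that decision.
- ECGs at Visit 3, Visit 10 and discontinuation are read centrally, and the central report includes HR (Sections 6.0 and 7.1.2.6).
- The siDMC trigger counts only discontinuations from blinded product, and the interim futility criteria use A1C and weight (Section 8.2.9).

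These help only in part. The ECGs are supine, are not scheduled at Visits 4 to 9, and are not named as a source for the HR endpoint. The confirmatory ECG is read by the principal investigator, who is unblinded for liraglutide, and it is done only once a criterion is already suspected, so it cannot correct a mean change.

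Three stronger readings are tempting but unsupported. One is that the liraglutide comparison is biased by some 41% or 81%. Those figures need a uniform, one-directional miscount in half or all of one arm, which nothing in the documents indicates. Another is that recounting until three readings agree within 5 bpm is a weakness of the manual option. That rule covers device readings too; it limits scatter within a set and neither creates nor removes a consistent shift. The third is that all HR results are compromised by open-label reading. MK-8521 versus placebo is not.

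**Conclusion.** The point holds as a gap in the measurement rule. Section 7.1.2.1 states a device requirement and then an unrestricted alternative to it, without a one-method rule or a record of the method. Two consequences follow from the text: possible within-subject mixing of methods, which adds noise in all arms, and possible unblinded observer reading in the liraglutide arm, which leaves MK-8521 versus liraglutide open to differential bias in HR change.

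The size cannot be determined. Under the assumed range in the working (a shift of 1 to 2 bpm in 25% to 100% of one arm's readings), the bias would be 0.25 to 2.0 bpm. If few readings are manual, it is negligible. The conclusion also assumes that the eCRF, which is not among the documents, does not already capture the HR method. The change is worth making because the remedy is cheap and, without a record of the method, nobody could later show that the problem did not occur.

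**What to change.** 1. Reconcile the two sentences in Section 7.1.2.1. The HR used for eligibility, baseline, discontinuation assessment and the HR endpoints should be the automated device value taken with the triplicate blood pressure. The clinical thresholds themselves are untouched.
2. Permit a manual count only when the device cannot give a valid reading.
3. Record the method in the eCRF for each triplicate set.
4. In Section 8.2.5.2, add a sensitivity analysis of HR change restricted to subjects with device readings at both baseline and Week 12. Centrally read ECG HR at Visits 3 and 10 can support it, with the supine position noted.

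A rule that a subject counted manually at Visit 3 must be counted manually throughout should not be added. It would secure consistency by locking in observer-read HR, including in the open-label arm.

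The cost is one reworded bullet, one eCRF field and one supplementary analysis. The device is already required at every visit where HR is measured, and hypotheses, sample size and visit schedule do not change. Sites lose a convenience.

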8.2.3 Analysis Endpoints

Efficacy and safety endpoints that will be evaluated for within- and/or between-treatment differences are listed below.

The primary time point of the study is Week 12.

The baseline value will be defined as the **Visit 3/Day 1** (Randomization) measurement. If this measurement is not available, the following pre-randomization measurement will be used as the baseline value.

Regimen at Visit 1/Screening	Baseline value		
On metformin monotherapy (no washout)	If the Visit 3 measurement is missing, the Visit 1 measurement will be used. If neither measurement is available, the baseline value will be treated as missing		
On dual therapy metformin and a second AHA (enter washout)	If the Visit 3 measurement is missing, the Visit 2 measurement will be used. If neither measurement is available, the baseline value will be treated as missing		

The mapping of relative day ranges to Week is provided in Section 12.4.

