Tier 2 ¹	Change from baseline in HR		X	X
	HR >100 bpm or HR increase >30 bpm		X	X
	AE summary measures		X	X
	Specific AEs ² , SOCs, specific confirmed CV SAEs, and PDLCs		X	X
Tier 3	All endpoints listed under Tier 2 (above) that have incidence <4 subjects in all treatment groups			X
	Additional hypoglycemia adverse event endpoints			X
	Change from baseline results (laboratory measurements, ECG, and vital signs)			X

¹ Non-continuous endpoints listed here will qualify for Tier 2 only if the incidence is ≥4 subjects in at least one of the treatment groups.

Analysis of Hypoglycemia

The Tier 1 analysis for hypoglycemia will include the numbers and percentages of subjects experiencing one or more adverse events of symptomatic hypoglycemia, regardless of glucose value.

The Tier 2 analysis for hypoglycemia will include the numbers and percentages of subjects experiencing one or more of each the following:

- Adverse events of hypoglycemia (symptomatic or asymptomatic), regardless of biochemical documentation.
- Adverse events of documented hypoglycemia, defined as adverse events of symptomatic hypoglycemia with a concurrent glucose measurement of <70 mg/dL (<3.9 mmol/L)

² Among those endpoints not pre-specified as Tier 1 endpoints.

AE=Adverse Event; CI=Confidence Interval; ECG=Electrocardiogram; PDLC=Pre-Defined Limit of Change;

SAE=Serious adverse event; SOC=System Organ Class; X = results will be provided.

Product: MK-8521

Protocol/Amendment No.: 004-02

 Adverse events of severe hypoglycemia, defined as adverse events of symptomatic hypoglycemia that required assistance, either medical or non-medical, regardless of whether such assistance was obtained, and regardless of biochemical documentation. These events will be further sub-classified as:

- Those that required medical assistance. Adverse events of symptomatic hypoglycemia that included a markedly depressed level of consciousness, loss of consciousness, or seizure will be classified as having required medical assistance, whether or not medical assistance was obtained
- Those that did not require medical assistance (i.e., those episodes that required non-medical assistance to treat).

The Tier 3 summary of hypoglycemia will include the following, based on episodes classified by the investigator as adverse events:

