12.4 Mapping of Relative Day Ranges to Weeks

The following will be used to map the relative day ranges to weeks, as described in **Section 8.2**.

Mapping of Relative Day Ranges to Weeks

Required Phase	Relative Day Range	Week
	Day Relative to Start of Trial	
_	Visit <2 and Day <1	$min(Day/7^{\dagger}, -2)$
Placebo Run-in	Visit ≥2 and Visit <3 and Day <1	-2
Placebo Run-in	Visit ≥3 and Day ≤1	0
Treatment	$2 \le \text{Day} \le 52$	6
Treatment	$53 \le \text{Day} \le 73$	9
Treatment	74 ≤ Day	12
† Truncated to the largest integer less than or equal to this ratio.		

Protocol/Amendment No.: 004-02

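### The Visit 2 heart rate and blood pressure readings are left out of the change-from-baseline analyses; adding them to the model as a second pre-randomization value would give a modest gain in precision at almost no cost

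*Combined protocol and SAP*

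**What the plan says.** Section 7.1.2.1 describes the method: "Vital sign measurements include a triplicate measurement of sitting blood pressure and heart rate", with one set of rules on rest, arm, cuff and caffeine for all visits. The flow chart (Section 6.0, footnote j) schedules these readings at Visits 1, 2 and 3 and at every later visit. Section 7.1.2.2 confirms that sitting values are taken at Visit 2 in addition to the postural ones, and exclusion criterion 38 needs a triplicate HR mean at that visit.

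For analysis, Section 7.1.2.1 assigns baseline HR to Visit 3: the mean of the last triplicate set "will be used to determine eligibility (Visit 1, Visit 2, and Visit 3), baseline HR (Visit 3), and discontinuation criteria (all post-randomization visits". Section 8.2.3 does the same for all endpoints ("The baseline value will be defined as the" Visit 3/Day 1 measurement) and turns to an earlier visit only as a substitute: "If this measurement is not available, the following pre-randomization measurement will be used as the baseline value". For subjects without washout, "If the Visit 3 measurement is missing, the Visit 1 measurement will be used"; for subjects with washout, "If the Visit 3 measurement is missing, the Visit 2 measurement will be used". Section 12.4 keeps Visit 2 data apart from Week 0: records with "Visit ≥2 and Visit <3 and Day <1" are mapped to Week -2.

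SBP and DBP are secondary endpoints analysed by the cLDA of Section 8.2.5.1, which has a single baseline in the response vector. In Section 8.2.5.2, Table 13 lists "Change from baseline in HR" as a Tier 2 endpoint with a between-group 95% CI. No model is named for this continuous endpoint.

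**The concern.** Sitting HR and BP vary from visit to visit. A second reading two weeks before randomization, taken by the same method, usually carries information about a subject's usual level that one reading misses. Here that reading is scheduled for every subject, and it enters the HR and BP change analyses only as a substitute for a missing Visit 3 value in washout subjects.

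What is at stake is the width of the intervals for two groups of endpoints. HR increase is one of the two potential safety issues named in Section 4.1.2.2, and change in HR is also part of the interim review in Section 8.2.9.2. SBP and DBP are secondary efficacy endpoints. With about 40 subjects per arm the intervals will not be narrow. HR is the more exposed of the two because, with no model named, an unadjusted change score is possible.

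**Working it through.** **Inputs from the plan (Section 8.2.7).** 40 subjects per arm; cumulative attrition 0.08 at Week 6 and 0.16 at Week 12; conditional Week 6 to Week 12 correlation 0.76732 (for A1C); A1C conditional SD 1.1%; difference 0.8%; two-sided alpha 0.05.

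**The plan's own figure.** Effective n = 1 / [0.76732²/(40×0.92) + (1−0.76732²)/(40×0.84)] = 1 / [0.5888/36.8 + 0.4112/33.6] = 35.4 (stated: 35). With n = 35, A1C power is 86% by the normal formula and 85% by the noncentral t (stated: about 85%). The plan's figure is reproduced. It gives no power, SD, correlation or interval width for HR or BP, so everything below rests on assumed values.

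**Visit 3 alone against Visits 2 and 3 in a baseline-adjusted model.** Assume the same correlation ρ between any two visits. The residual variance, as a fraction of the total, is

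- Visit 3 only: 1 − ρ²
- Visits 2 and 3: 1 − 2ρ²/(1+ρ)

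The ratio of standard errors is therefore √(1+2ρ)/(1+ρ), and the equivalent gain in subjects is (1+ρ)²/(1+2ρ) − 1.

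| ρ (assumed) | SE ratio | CI narrower by | Equivalent extra subjects |
|---|---|---|---|
| 0.4 | 0.958 | 4.2% | 8.9% |
| 0.5 | 0.943 | 5.7% | 12.5% |
| 0.6 | 0.927 | 7.3% | 16.4% |
| 0.7 | 0.911 | 8.9% | 20.4% |
| 0.8 | 0.896 | 10.4% | 24.6% |

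**If Visit 2 predicts Week 12 less well than Visit 3 does.** Assume a correlation of 0.7 between Visits 2 and 3, and 0.6 between Visit 3 and Week 12.

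- Visit 2 to Week 12 = 0.55: R² = (0.36 + 0.3025 − 2×0.6×0.55×0.7)/(1 − 0.49) = 0.393. SE ratio = √(0.607/0.64) = 0.974, so the interval is 2.6% narrower.
- Visit 2 to Week 12 = 0.42 (= 0.7×0.6, so Visit 2 adds nothing given Visit 3): R² = 0.36, SE ratio 1, no gain.

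**Why not average the two visits.** In the second of these cases, a change score from the two-visit mean has variance 1 + 0.85 − 2×0.51 = 0.83, against 2×(1 − 0.6) = 0.80 from Visit 3 alone. The interval becomes √(0.83/0.80) = 1.019 times as wide. An ANCOVA on the average does worse: √[(1 − 0.51²/0.85)/0.64] = 1.041. Two separate terms in the model avoid this.

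**HR illustration.** Assume SD 9 bpm, ρ = 0.6, effective n 35.4 and a multiplier of 1.98. The common factor is 1.98×9×√(2/35.4) = 4.24.

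- Unadjusted change from Visit 3: 4.24×√0.8 = 3.8 bpm
- Adjusted for Visit 3: 4.24×√0.64 = 3.4 bpm
- Adjusted for Visits 2 and 3: 4.24×√0.55 = 3.1 bpm

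Before rounding, the half-widths are 3.79, 3.39 and 3.14. Adjusting for Visit 3 supplies 0.40 of the total 0.65 bpm, and Visit 2 supplies the remaining 0.25.

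**The case against.** The last pre-dose value is a coherent, prespecified baseline, and no stated target depends on changing it. That stands: this is an improvement on offer, not an error.

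There are also reasons to doubt equal correlation. Visit 2 comes before the placebo-injection run-in. For subjects without washout it is also the visit at which diet and exercise counseling starts. The four-week stability rule for BP medication is counted back from Visit 3, so an adjusted regimen may be only two weeks old at Visit 2. This also stands, and it is why the range has to reach down to zero.

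Four stronger readings are tempting, and the documents do not support them.

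- *The intervals would be 13% narrower.* That figure is √(1.5/2) = 0.866. It holds only for an unadjusted change score taken from a two-visit average under equal correlation. The BP analysis already conditions on Visit 3 through the cLDA, and for HR no model is stated.
- *Visit 3 is distorted because HR had to be 88 bpm or below on that day.* Exclusion criteria 22 and 38 apply the same limit at Visits 1 and 2. The selection precedes randomization and does not bias the comparison between arms.
- *The gain would resolve the 2.46 bpm difference from liraglutide in P003.* That was a 24-hour time-weighted mean in domiciled subjects, not a sitting clinic value. None of the illustrated half-widths falls below it in any case.
- *HR is the main safety endpoint or decides between the doses.* HR change is Tier 2, Tier 1 is symptomatic hypoglycemia, and Section 4.2.2 gives dose-response in both safety and efficacy as the reason for two doses.

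The illustration also borrows an effective n built on A1C correlations. An unadjusted analysis of Week 12 completers would have 40×0.84 = 33.6 per arm, which moves 3.8 to about 3.9 bpm.

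**Conclusion.** The point holds as a modest and nearly free gain in precision for a Tier 2 safety endpoint and for secondary BP endpoints. Relative to a model that adjusts for Visit 3 alone, the expected narrowing is about 4% to 10% for assumed equal correlations of 0.4 to 0.8, about 3% if Visit 2 is somewhat less predictive, and nothing if it is uninformative given Visit 3. For HR, naming a baseline-adjusted model at all may matter more than adding Visit 2. Both values precede randomization, so using them cannot bias the arm comparison. The gain applies to continuous change only; the proportion with HR above 100 bpm does not use a baseline.

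**What to change.** - Keep Visit 3 in Section 8.2.3 as the baseline that defines change and the category of HR increase above 30 bpm in Table 13. The clinical HR criteria in Section 5.9 are not part of this point and stay as written.
- In Section 8.2.5.1 (SBP, DBP) and Section 8.2.5.2 (continuous HR change), specify either the cLDA with Week -2 added as a second pre-randomization time point with a common mean across arms, or ANCOVA with the Visit 2 and Visit 3 values as separate covariates. State that the two visits are not averaged.
- State how a missing Visit 3 value is handled in these models. Under the present substitution rule, a washout subject's Visit 2 value would otherwise enter twice, as Week 0 and as Week -2.

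The cost is a few sentences and some programming, with no new data or visits. If the cLDA uses the weeks in Section 12.4, the unstructured covariance grows from 4 to 5 time points, that is from 10 to 15 parameters; the ANCOVA route costs one degree of freedom. The change should be made before the interim data are unblinded.
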